9.2. Details on Selected PRO Endpoints

AAPPO

The AAPPO is a 11-item scale. Items 1-4 are an assessment of current hair loss, eyebrow loss, eyelash loss and body hair loss and will be as such analyzed separately on a scale of 0-4, with 0 =‘no hair loss’ and 4=‘complete hair loss’. Items 5-8 are an assessment of emotional symptoms. Response choices on these items are scored from 0 =‘never’ to 4=‘always’. Items 9-11 are an assessment of activity limitations. Response choices on these items are scored from 0=‘not at all’ to 4= ‘completely’.

- AAPPO Items 1 through 4 are scored separately as 0=‘no hair loss’, 1=‘little hair loss’ and 2-4=‘moderate-complete hair loss’.
- Improvement on AAPPO items (1-4) among participants with a baseline score 2-4, indicating moderate-complete hair loss who achieved a score of 0=‘no hair loss’ or 1=‘little hair loss’.
- Emotional Symptoms: Mean of Items 5, 6, 7, 8 (missing rule: requires at least 2 non-missing responses; otherwise missing).
- Activity Limitations: Mean of Items 9, 10, 11 (missing rule: requires at least 2 non-missing responses; otherwise missing).

AARU:

- Assessment of total in-person and remote healthcare visits.
- Assessment of AA-related in-person and remote healthcare visits.
- Assessment of utilization of hair prostheses or camouflaging agents.
- Assessment of # of days hair prostheses or camouflaging agents were utilized.
- Percentage of patients not currently employed.
- Percentage of patients who have not sought employment due to alopecia areata.
- Number of opportunities for employment not sought due to alopecia areata.

WPAI –AA:

WPAI-AA is an adaptation of the WPAI:SHP (Specific Health Problem) version. Outcomes from this scale are expressed as impairment percentages, with higher numbers indicating greater impairment and less productivity. The questionnaire is scored as follows:

Questions:

- 1 = currently employed.

- 2 = hours missed due to specified problem.
- 3 = hours missed other reasons.
- 4 = hours actually worked.
- 5 = degree problem affected productivity while working.
- 6 = degree problem affected regular activities.

Scoring.

- Multiply scores by 100 to express in percentages.
- Percent work time missed due to problem (Absenteeism): $Q2/(Q2+Q4)$.
- Percent impairment while working due to problem (Presenteeism): $Q5/10$.
- Percent overall work impairment due to problem (Overall Work Impairment): $Q2/(Q2+Q4)+[(1-(Q2/(Q2+Q4)))x(Q5/10)]$.
- Percent activity impairment due to problem (Activity Impairment): $Q6/10$.

9.3. Laboratory Data Criteria for Discontinuation and Abnormalities

Labs Meeting Discontinuation Criteria, as per Appendix 3.2 of the protocol

Table 7. Laboratory Values Meeting Discontinuation Criteria

		Criterion #1	Criterion #2
Hematology	Hemoglobin	<90 g/L or a decrease of >30% from baseline	n/a
	Platelets	<75 × 10 ⁹ /L	n/a
	Lymphocytes (ABSOLUTE)	<0.5 × 10 ⁹ /L	n/a
	Neutrophils (ABSOLUTE)	<0.75 × 10 ⁹ /L	n/a
Chemistry	Aspartate Aminotransferase	>3× ULN W/Bilirubin >2× ULN	Two Sequential Elevations >5× ULN
	Alanine Aminotransferase	>3× ULN W/Bilirubin >2× ULN	Two Sequential Elevations >5× ULN
	Creatine Kinase	>10× ULN	

Lab Test Abnormalities

Table 8. Laboratory Test Abnormalities

		Lower Limit	Upper Limit
Hematology	Hemoglobin	<0.8× LLN	n/a
	Hematocrit	<0.8× LLN	n/a
	Red Blood Cell Count	<0.8× LLN	n/a
	MCV	<0.9× LLN	>1.1× ULN
	MCH	<0.9× LLN	>1.1× ULN
	MCHC	<0.9× LLN	>1.1× ULN
	Platelets	<0.5× LLN	>1.75× ULN
	White Blood Cell Count	<0.6× LLN	>1.5× ULN
	Reticulocytes	<0.5× LLN	>1.5× ULN
	Reticulocytes/Erythrocytes	<0.5× LLN	>1.5× ULN
	Leukocytes	<0.6× LLN	>1.5× ULN
	Lymphocytes (ABSOLUTE)	<0.8× LLN	>1.2× ULN
	Lymphocytes/Leukocytes	<0.8× LLN	>1.2× ULN
	Neutrophils (ABSOLUTE)	<0.8× LLN	>1.2× ULN
	Neutrophils/Leukocytes	<0.8× LLN	>1.2× ULN
	Basophils/Leukocytes	n/a	>1.2× ULN
	Eosinophils	n/a	>1.2× ULN
	Eosinophils/Leukocytes	n/a	>1.2× ULN
	Monocytes	n/a	>1.2× ULN
	Monocytes/Leukocytes	n/a	>1.2× ULN
Prothrombin Time	n/a	>1.1× ULN	
Basophils	n/a	>1.2× ULN	

Table 8. Laboratory Test Abnormalities

		Lower Limit	Upper Limit
	Prothrombin Intl. Normalized Ratio	n/a	>1.1× ULN
Chemistry	Blood Urea Nitrogen	n/a	>1.3× ULN
	Urea	n/a	>1.3× ULN
	Creatinine	n/a	>1.3× ULN
	Glucose	<0.6× LLN	>1.5× ULN
	Calcium	<0.9× LLN	>1.1× ULN
	Sodium	<0.95× LLN	>1.05× ULN
	Potassium	<0.9× LLN	>1.1× ULN
	Chloride	<0.9× LLN	>1.1× ULN
	Bicarbonate	<0.9× LLN	>1.1× ULN
	Aspartate Aminotransferase	n/a	>3.0× ULN
	Alanine Aminotransferase	n/a	>3.0× ULN
	Bilirubin	n/a	>1.5× ULN
	Direct Bilirubin	n/a	>1.5× ULN
	Indirect Bilirubin	n/a	>1.5× ULN
	Alkaline Phosphatase	n/a	>3.0× ULN
	Uric Acid	n/a	>1.2× ULN
	Albumin	<0.8× LLN	>1.2× ULN
	Creatine Kinase	n/a	>2.0× ULN
	Cholesterol	n/a	>1.3× ULN
	HDL Cholesterol	<0.8× LLN	n/a
LDL Cholesterol	n/a	>1.2× ULN	
Triglycerides	n/a	>1.3× ULN	
Protein	<0.8× LLN	>1.2× ULN	
Gamma Glutamyl Transferase	n/a	>3.0× ULN	
Urinalysis	pH (Scalar)	<4.5	>8
	Glucose (Scalar)	n/a	≥1
	Ketones (Scalar)	n/a	≥1
	Protein (Scalar)	n/a	≥1
	Hemoglobin (No Unit)	n/a	≥1
	Nitrite (No Unit)	n/a	≥1
	Leukocyte Esterase (No Unit)	n/a	≥
	Urobilinogen	n/a	≥1
	Erythrocytes (Scalar)	n/a	≥20
	Leukocytes (Scalar)	n/a	≥20
	Epithelial Cells (Scalar)	n/a	≥6
	Granular Casts (Scalar)	n/a	>1
	Hyaline Casts (Scalar)	n/a	>1
	Bacteria (No Unit)	n/a	>20

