### Laboratory Abnormalities:

All the following laboratory abnormalities **require discontinuation** if they are confirmed by re-test. Refer to the associated re-testing timeframes for laboratory abnormalities in [Appendix 3.1](#):

- Absolute Neutrophil Count <750/mm^3 (<0.75 × 10^9/L).
- Hemoglobin <9.0 g/dL (<5.59 mmol/L or <90 g/L) or a decrease of >30% from baseline (either criterion or both).
- Platelet count <75,000/mm^3 (<75.0 × 10^9/L).
- Absolute Lymphocyte Count <500/mm^3 (<0.5 × 10^9/L).

NOTE: Subjects with absolute lymphocyte count <500/mm^3 (0.5 × 10^9/L) will be reflex tested for FACS-TBNK until the absolute lymphocyte count resolves or stabilizes at a level acceptable to the investigator and sponsor.

- Creatine kinase  $>10 \times$  ULN.

NOTE: In addition to re-testing creatine kinase  $>3 \times$  ULN, urine myoglobin will be performed as reflex testing for any subject with creatine kinase  $>10 \times$  ULN.

- Aspartate aminotransferase (AST) or alanine aminotransferase (ALT) that meet ANY of the following:
  - $>3$  times the upper limit of normal with at least one total bilirubin value  $>2$  times the upper limit of normal;
  - $>3$  times the upper limit of normal accompanied by signs or symptoms consistent with hepatic injury (eg, new onset elevated PT/INR);
  - Two sequential AST or ALT elevations  $>5$  times the upper limit of normal, regardless of total bilirubin or accompanying signs or symptoms.

NOTE: In each case, there is a need for additional investigations, such as review of ethanol, recreational drug and dietary supplement consumption; testing for acute hepatitis A, B or C infection and biliary tract imaging should be promptly discussed with the sponsor or designee.

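### SAP Table 7 is labelled as the protocol's Appendix 3.2 laboratory discontinuation criteria, but leaves out the re-test condition and one of the three AST/ALT criteria

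*SAP*

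**What the plan says.** Protocol Appendix 3.2, under Laboratory Abnormalities, lists the values that require discontinuation "if they are confirmed by re-test" and refers to Appendix 3.1 for the re-test timing: within one week for hematology and creatine kinase, within 48 hours for AST, ALT and bilirubin. It gives three alternative AST/ALT criteria:

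- above 3 "times the upper limit of normal with at least one total bilirubin value" above 2 × ULN;
- above 3 "times the upper limit of normal accompanied by signs or symptoms consistent with hepatic injury (eg, new onset elevated PT/INR");
- as the third alternative, "Two sequential AST or ALT elevations" above 5 × ULN, whatever the bilirubin or clinical signs.

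SAP Section 9.3 heads its Table 7 "Labs Meeting Discontinuation Criteria, as per Appendix 3.2 of the protocol". For AST and for ALT the table gives two entries: ">3× ULN W/Bilirubin >2× ULN" and "Two Sequential Elevations >5× ULN". Hemoglobin, platelets, absolute lymphocytes, absolute neutrophils and creatine kinase appear as thresholds alone.

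SAP Section 6.7.2 plans frequencies and percentages of clinically significant laboratory abnormalities and sends the reader to Section 9.3 for the criteria. It does not say whether a Table 7 flag needs one value or a confirmed value.

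**The concern.** A table that names its source should reproduce that source. SAP Section 2 allows the SAP to modify the protocol's plans, but a table marked as following Appendix 3.2 declares no modification, so the two texts simply disagree.

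The layout makes the gap matter. Table 7 writes out a repeat for one entry (two sequential elevations) and for no other. A programmer working from it would naturally flag a single low platelet or lymphocyte count as meeting the protocol's discontinuation criteria, although under Appendix 3.2 a value that recovers on re-test does not. Conversely, a subject who meets only the omitted AST/ALT criterion would get no flag.

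What is at stake is the accuracy of a safety summary. The incidence of clinically significant laboratory abnormalities is a safety endpoint (SAP Section 3.4), and protocol Section 9.5 plans an analysis of safety events that trigger withdrawal. Subject management follows the protocol and is not affected.

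**Working it through.** The plan states no expected count, so there is no figure to reproduce. The check is a criterion-by-criterion comparison after converting units.

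| Criterion | Protocol Appendix 3.2 | SAP Table 7 | Same cut-off? | Repeat stated in Table 7? |
|---|---|---|---|---|
| Hemoglobin | < 9.0 g/dL × 10 = 90 g/L, or fall > 30% | < 90 g/L, or fall > 30% | yes | no |
| Platelets | < 75,000/mm³ ÷ 1,000 = 75 × 10⁹/L | < 75 × 10⁹/L | yes | no |
| Lymphocytes | < 500/mm³ ÷ 1,000 = 0.5 × 10⁹/L | < 0.5 × 10⁹/L | yes | no |
| Neutrophils | < 750/mm³ ÷ 1,000 = 0.75 × 10⁹/L | < 0.75 × 10⁹/L | yes | no |
| Creatine kinase | > 10 × ULN | > 10 × ULN | yes | no |
| AST/ALT with bilirubin | > 3 × ULN with bilirubin > 2 × ULN | same | yes | no |
| AST/ALT with clinical signs or symptoms | > 3 × ULN | absent | – | – |
| AST/ALT, two in sequence | > 5 × ULN | same | yes | built into the criterion |

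Of 8 protocol criteria, 7 are carried over, all with identical cut-offs, and 1 is absent. The general re-test condition is stated for none. One of the 7 contains its own repeat, so 7 − 1 = 6 are affected.

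**Direction.** Everyone with a confirmed crossing also has a single crossing. For the six affected criteria, dropping confirmation can therefore only add subjects. Dropping a criterion can only remove them. The net direction is not determined.

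**Size (illustration only).** Let q be the chance that a scheduled draw gives an isolated crossing that re-test would not confirm. The documents do not give q; it is an assumption here. With n independent draws of one analyte, the share of subjects with at least one such crossing is 1 − (1 − q)ⁿ. The Schedule of Activities has 6 post-baseline hematology draws to Week 24 (Weeks 2, 4, 8, 12, 18, 24). It has 12 in all when Weeks 26, 28, 34, 40, 48 and the follow-up visit are added. For a 120-subject arm:

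| q per draw | n = 6 | n = 12 |
|---|---|---|
| 0 | 0 | 0 |
| 0.05% | 0.3% (0.4 subjects) | 0.6% (0.7) |
| 0.1% | 0.6% (0.7) | 1.2% (1.4) |
| 0.5% | 3.0% (3.6) | 5.8% (7.0) |

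For example, q = 0.1% and n = 12 give 1 − 0.999¹² = 1.19%, and 120 × 0.0119 = 1.4. The range starts at zero.

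**Where it could arise.** Lymphocytes are a plausible case. The protocol reports a mean fall of 24% during 200 mg dosing in the Phase 2a alopecia study (Section 1.4.1), and exclusion criterion 24 admits counts down to 0.8 × 10⁹/L. A fall of that size from there gives 0.8 × (1 − 0.24) = 0.61, not far above 0.5. This does not supply a value for q.

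**Are re-tests available?** For hematology and creatine kinase, every discontinuation threshold lies inside an Appendix 3.1 re-test trigger: neutrophils 750 against 1,000/mm³; platelets 75,000 against 100,000/mm³; lymphocytes 500 against 600/mm³; creatine kinase 10 against 3 × ULN; hemoglobin 9.0 against 10.0 g/dL. The trigger of a hemoglobin fall of at least 2.0 g/dL also covers a fall above 30%: from the lowest eligible screening value, 11.0 g/dL, 30% is 3.3 g/dL. For AST, ALT and bilirubin, Appendix 3.1 asks for re-testing of values covered by protocol Section 8.4.2.

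**The case against.** The strongest reply is that the heading cites Appendix 3.2, so the re-test rule applies by reference and a careful programmer would look it up. That reading is open: the SAP is silent on single versus confirmed values and does not specify single values. It is weakened because the table spells out a repeat in one place only.

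A reader might infer that the reported count will be wrong, or will be too high. The documents do not support that. Section 6.7.2 points to Section 9.3 for criteria but nowhere expressly commits to counting subjects from Table 7. No rate of transient values is given, and the two omissions pull in opposite directions.

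A reader might also infer that subjects rightly kept on treatment will look like missed stops. No planned output crosses Table 7 with disposition, so that too goes beyond the text.

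Nor would a liver case necessarily go unreported. The omitted criterion depends on clinical signs or symptoms, which laboratory data alone cannot supply; this may explain why it was left out. SAP Table 8 has rows for AST and ALT above 3 × ULN, prothrombin time and INR. Protocol Section 8.2.2 requires an abnormal result with symptoms, or one leading to discontinuation, to be recorded as an adverse event, and SAP Section 6.7.1 summarizes adverse events leading to discontinuation. Such a case would lack only a Table 7 flag.

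What stands after all this is the mismatch itself: the label says one thing and the contents another.

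**Conclusion.** The point holds as an inconsistency between protocol and SAP. Table 7 omits the re-test condition for six criteria and leaves out one of three AST/ALT criteria, while its heading says it follows Appendix 3.2. A summary of subjects meeting protocol discontinuation criteria that is built from the table may be misstated in either direction, by an amount that cannot be calculated from the documents and may be nil.

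This rests on two assumptions: that such a summary is produced from Table 7, and that the table is programmed as written. It is a minor reporting matter. No efficacy conclusion depends on it, and nothing here bears on which clinical stopping rule is right.

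**What to change.** Reconcile Table 7 with Appendix 3.2 before unblinding, in one of two ways.

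1. **Match the protocol.** Derive the flag from values confirmed by the Appendix 3.1 re-test, state how a missing or late re-test is handled, and show any single crossing separately. State how the third AST/ALT criterion is captured: from PT/INR where available, otherwise from adverse event or discontinuation data. PT/INR is not in the routine panel (protocol Table 3); it belongs to the work-up of potential liver injury in Section 8.4.2. Derive the flag before visit windowing. SAP Section 9.1 keeps one observation per window for summary tables, so a Day 29 value and its re-test a week later (Day 36) both fall in the Week 4 window (Days 22 to 42) and only one would survive.
2. **Relabel.** Retitle Table 7 as single values crossing the listed thresholds, remove the statement that it follows Appendix 3.2, and note that the AST/ALT criterion involving signs or symptoms is not included.

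The first option costs a modest extra derivation, since Appendix 3.1 already calls for the re-tests, plus some clinical review for the third AST/ALT criterion. The second is a text change. Neither needs new data collection.

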9.4. List of Countries by Region

Table 9. Countries by Region

Region	Countries
North America	Canada, United States
Europe	Czech Republic, Germany, Hungary, Poland, Russia, Spain, United Kingdom
Asia	China, Japan, South Korea, Taiwan
Rest of World	Australia, Argentina, Chile, Colombia, Mexico

9.5. List of Targeted Medical History Terms

Table 10. Targeted Medical History Terms

Term	PT
Atopic dermatitis	DERMATITIS ATOPIC
Diabetes mellitus Type I	TYPE 1 DIABETES MELLITUS
Crohn's disease	CROHN'S DISEASE
Ulcerative colitis	COLITIS ULCERATIVE
Systemic lupus erythematosus	SYSTEMIC LUPUS ERYTHEMATOSUS
Sjogren's syndrome	SJOGREN'S SYNDROME
Rheumatoid arthritis	RHEUMATOID ARTHRITIS
Psoriatic arthritis	PSORIATIC ARTHROPATHY
Psoriasis	PSORIASIS
Vitiligo	VITILIGO
Hashimoto's thyroiditis	AUTOIMMUNE THYROIDITIS
Graves' disease	BASEDOW'S DISEASE

9.6. Tipping Point Analysis for Binary Data

The primary endpoint for the study and for the FDA/PMDA is response based on SALT ≤ 20 (a binary endpoint) at Week 24; for the EMA and competent authorities in the VHP countries the primary endpoint is response based on SALT ≤ 10 at Week 24. This tipping point analysis will be conducted for both endpoints, with a subtle difference: while the analysis for the study and for the FDA/PMDA will treat missing as MNAR regardless of the reason for missingness, the analysis for the EMA will treat missing due to COVID-19 as MNAR but missing due to other reasons will be considered as non-responders.

Treatment comparisons are performed for each PF-06651600 dose group versus placebo. These binary endpoints are also assessed at post-baseline visits of Weeks 4, 8, 12, and 18. And are coded as a numeric variable with values of 1 if SALT score is ≤ 20 or 0 if SALT score is > 20 . When there is insufficient information to evaluate the endpoint at a visit (eg, due to discontinuation of study participation or other reasons), they will be coded as

missing at that visit. Tipping point analysis is used to evaluate the impact of these missing values on the trial conclusion based on the primary endpoints. Since the focus is on the Week 24 visit, this analysis will use longitudinal data of these endpoints from Week 4 up to Week 24 only (5 post-baseline visits) without imputation of the missing responses. Data of visits after Week 24 will not be included in these analyses.

A SAS macro “alopbinarytippingV2.sas” (Version 2) is developed to fit the purpose of implementing the tipping point analysis for this study. Longitudinal data of the endpoints are imported into the macro.

The prior density specified for the baseline logit is Normal(-1.7, sd=3) and those for all other logit effect parameters are Normal(0, sd=1). This gives the prior median and mean of 15% and 32% respectively for the probability of response (SALT ≤20) for the placebo group at the post-baseline visits. The prior density for variance of random effects is Inverse-Gamma(shape=1, scale=1). In this prior, the prior 90th percentile for σ^2 is approximately 9.

The following values will be specified for the implementation of the analyses for each of the active treatment and placebo groups.

- Active treatment group: deltac = -0.5, -0.3, -0.1, 0, 0.1, 0.3, 0.5 (7 of them)
- Placebo group: deltac = -0.9, -0.7, -0.5, -0.3, -0.1, 0 (6 of them)

Since the delta value is subtracted from the MAR probability, a negative delta value means favoring the probability; a positive delta value means penalizing the probability; and a 0 value means the same MAR probability. The values of these sensitivity parameters (deltac, deltac) may be adjusted if needed.

The number of imputations/imputed datasets per combination of sensitivity parameters for the tipping point analysis will be at least 100.

The seeds used for tipping point analysis are defined below:

Endpoint	Seed for MCMC (seed4mcmc)	Seed for imputation (seed4imp)
Response based on SALT ≤20	3355	6688
Response based on SALT ≤10	1286	9276
PGI-C Response	4562	1520

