**Table 6. Statistical Methods for the Analysis of the Primary Endpoint for the Overall Study, and for the FDA/PMDA**

Analysis #	Analysis Designation	Statistical Method	Approach for missing data due to COVID-19	Approach for missing data due to other reasons
1	Primary	MN	Exclude missing	Consider missing as non-responders
2	Supplementary	GLMM	MAR	MAR
2a	Supplementary	GLMM/ Tipping point	MNAR	MNAR
3	Supplementary	MN	Consider missing as non-responders	Consider missing as non-responders

Abbreviations: GLMM = generalized linear mixed model; MN = Miettinen and Nurminen; MAR = Missing at random; MNAR = Missing not at random

In the primary analysis for the overall study, and for the FDA/PMDA, the primary endpoint will be analyzed by the MN method for the difference in the proportion of responders between each active treatment group and placebo. Subjects with missing SALT score at Week 24 due to COVID-19 related reasons will be excluded from the analysis at that time point, whereas missing data due to other reasons will be counted as non-responders at that time point (Analysis 1). As a supplementary analysis to assess the impact of COVID-19-related missing data on the results of the primary analysis, the analysis of the primary endpoint will be repeated with all missing data considered as non-responders regardless of the reason for missingness (Analysis 3).

As a supplementary analysis a GLMM for the longitudinal binary data of SALT  $\leq 20$  response over time up to Week 24 will be conducted (Analysis 2) to evaluate the impact of the missing data approach to the primary conclusion. In this analysis, two different missing mechanisms will be assumed: MAR and MNAR. A tipping point analysis will be conducted under MNAR (Analysis 2a).

The key secondary endpoint for the overall study (SALT  $\leq 10$  response at Week 24) will be analyzed using the same approach as Analysis 1. Analysis 4 described in Table 7 will also be conducted for this endpoint as supplementary.

**9.2.2.2. For the EMA and Competent Authorities in the VHP Countries (Analysis of the Primary and Key Secondary Endpoints)**

For the EMA and competent authorities in the VHP countries, the SALT  $\leq 10$  response at Week 24 will be the primary endpoint and the PGI-C response at Week 24 will be analyzed as a key secondary endpoint. The testing procedures are described in Section 9.2.1.3, and the planned analysis of the primary endpoint are described in Table 7.

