**Table 7. Statistical Methods for the Analysis of the Primary Endpoint for the EMA and Competent Authorities in the VHP Countries**

Analysis #	Analysis Designation	Statistical Method	Approach for missing data due to COVID-19	Approach for missing data due to other reasons
4	Primary	GLMM	MAR	Consider missing as non-responders
4a	Supplementary	GLMM/ Tipping point	MNAR	Consider missing as non-responders
1	Supplementary	MN	Exclude missing	Consider missing as non-responders
3	Supplementary	MN	Consider missing as non-responders	Consider missing as non-responders

Abbreviations: GLMM = generalized linear mixed model; MN = Miettinen and Nurminen; MAR = Missing at random; MNAR = Missing not at random

The primary analysis of the primary endpoint for the EMA and competent authorities in the VHP countries (Analysis 4) will be conducted using a GLMM model for the longitudinal binary data of SALT  $\leq 10$  response over time up to Week 24, assuming a missing mechanism of MAR for missing data due to COVID-19. Missing data due to reasons not related to COVID-19 will be assumed as non-responders. The key secondary endpoint will also be analyzed using this approach.

As a supplementary analysis, imputations will be implemented under the framework of the same GLMM model as above, using a tipping point analysis (Analysis 4a). For this analysis,

the assumption of the missing mechanism for this analysis will be MNAR for cases of missing data due to COVID-19, and missing data due to other reasons will be considered as non-responders.

Additional supplementary analyses will use the MN method to estimate 95% CIs and p-values for the differences in the proportions of response between each active treatment group and placebo. In Analysis 1 missing data due to COVID-19 will be excluded from the analysis, whereas missing data due to other reasons will be considered as non-responders. In Analysis 3, all missing data will be considered as non-responders, regardless of the reason for missingness.

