5.2.1.2. Generalized Linear Mixed Model and Tipping Point – Analyses 2 and 2a

As a supplementary analysis, the primary endpoint for the overall study and for the FDA/PMDA will also be analyzed utilizing a generalized linear mixed model (GLMM) for longitudinal binary data of response based on $SALT \leq 20$ over time up to Week 24. This binary outcome will be modeled using a logistic-normal distribution. Fixed factors in this model are treatment (6 levels), visit (5 levels) and treatment-by-visit interaction. Visit will be modeled as a categorical covariate. A subject-specific random intercept will be used to model the correlation within a subject over time. Due to the expected negligible placebo response, a Bayesian estimation will be carried out in which diffusive priors will be used and the placebo response probability will be bounded away from 0 to avoid the potential convergence issues. From this model, one can derive the estimates of the marginal probability of response for each treatment group at each visit as well as inferential comparisons (the proportional difference between active and placebo groups, CIs and p-values) between treatment groups after the random effect is integrated out from the posterior samples. Given that this random intercept model specifies the full joint distribution for the outcome, the inference for the marginal proportions will be valid in the presence of missing data when the missing mechanism is missing at random (MAR). This inference will be with respect to the difference in treatments assuming all subjects maintained their randomized therapy. This analysis will be referred to as Analysis 2.

A tipping point analysis will be conducted under the assumption of missing not at random (MNAR). The imputations will be implemented under the framework of the same logit normal GLMM as above. Imputation of missing SALT response is performed only at Week 24 based on the predictive distribution of the GLMM. Under MNAR assumption, a fixed MNAR quantity (favorable or unfavorable), delta, will be applied to the probability of response at Week 24 for subjects with missing SALT response in the PF 06651600 dose groups and placebo group independently to assess when the conclusion might change (ie, tipping). Imputations will be repeated to obtain completed datasets. The Rubin's rules^{4,6} will be used to combine the results of multiple imputed samples for inference. This analysis will be referred to as Analysis 2a.

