5.2.1.3. Generalized Linear Mixed Model and Tipping Point – Analyses 4 and 4a

The primary analysis of the primary endpoint for the EMA and competent authorities in the VHP countries will be based on a MAR assumption and use multiple imputation methods similar to those described in [Section 5.2.1.2](#). In this analysis, while subjects with missing SALT scores due to COVID-19 will be assumed to be MAR, subjects with missing SALT scores due to other reasons will be treated as non-responders. This analysis will be referred to as Analysis 4.

A tipping point analysis will be conducted similar to that described in [Section 5.2.1.2](#). While the analysis for the study and for the FDA/PMDA will treat missing as MNAR regardless of the reason for missingness, the analysis for the EMA will treat missing due to COVID-19 as MNAR but missing due to other reasons will be considered as non-responders. This analysis will be referred to as Analysis 4a.

The key secondary endpoint, PGI-C response at Week 24, will also be analyzed using this approach.

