5.3.1. Binary Endpoints

The same rule will be used for any missing data whether it is a missed visit, or it is a missing value due to early discontinuation. Depending on the analysis and the endpoint being analyzed, the following approaches will be used for managing missing data in binary endpoints:

- a. Subjects with missing SALT scores due to COVID-19 in a given visit will be excluded from the analysis at that timepoint, whereas subjects with missing SALT scores due to other reasons will be treated as non-responders at that timepoint (Analysis 1, [Section 5.2.1.1](#)).
- b. Subjects with missing SALT scores due to any reason in a given visit will be treated as non-responders at that timepoint (Analysis 3, [Section 5.2.1.1](#)).
- c. Imputation of missing SALT response at Week 24 is performed based on the predictive distribution of the GLMM under MAR (Analysis 2, [Section 5.2.1.2](#)).

- d. Imputation of missing SALT response at Week 24 is performed based on the predictive distribution of the GLMM under MNAR using tipping point analysis (Analysis 2a, [Section 5.2.1.2](#)).
- e. Imputation of missing SALT response is performed based on the predictive distribution of the GLMM under MAR for subjects with missing data due to COVID-19, whereas subjects with missing SALT scores due to other reasons will be treated as non-responders at that timepoint (Analysis 4, [Section 5.2.1.3](#)).
- f. Imputation of missing SALT response is performed based on the predictive distribution of the GLMM under MNAR using tipping point analysis for patients with missing data due to COVID-19, whereas subjects with missing SALT scores due to other reasons will be treated as non-responders at that timepoint (Analysis 4a, [Section 5.2.1.3](#)).

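### SAP 5.2.1.2 promises diffuse priors for the GLMM, but SAP 9.6 sets sd 1 on every treatment, visit and interaction logit; read from the model, Analysis 2 then loses about 2 to 9 of a planned 24 points

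*SAP*

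**What the plan says.** SAP 5.2.1.2 defines a logit-normal model with fixed treatment (6 levels), visit (5 levels) and treatment-by-visit effects and a random subject intercept. Of the fit it says "a Bayesian estimation will be carried out in which diffusive priors will be used".

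SAP 9.6 is the only place where numbers are given: "The prior density specified for the baseline logit is Normal(-1.7, sd=3) and those for all other logit effect parameters are Normal(0, sd=1"). It adds a prior median of 15% and mean of 32% for placebo response, and an Inverse-Gamma(1, 1) prior for the random-intercept variance with a 90th percentile near 9.

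How the model is used is described in two ways:

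- **Analysis 2** (supplementary, SALT ≤20). SAP 5.2.1.2 reads it from the posterior: "one can derive the estimates of the marginal probability of response for each treatment group at each visit as well as inferential comparisons". SAP 5.3.1(c) describes imputation: "Imputation of missing SALT response at Week 24 is performed based on the predictive distribution of the GLMM under MAR (Analysis 2".
- **Analysis 4** (EMA primary, SALT ≤10). Protocol 9.2.2.2 says only that it "will be conducted using a GLMM model for the longitudinal binary data of SALT" ≤10. SAP 5.2.1.3 says it "will be based on a MAR assumption and use multiple imputation methods similar to those described in" 5.2.1.2, and 5.3.1(e) agrees: "Imputation of missing SALT response is performed based on the predictive distribution of the GLMM under MAR for subjects with missing data" due to COVID-19.

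Protocol 9.2.2.1 gives the purpose of Analysis 2: "to evaluate the impact of the missing data approach to the primary conclusion".

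**The concern.** On the logit scale, Normal(0, sd 1) on a treatment contrast is an informative prior centred on no effect. In SAP 5.2.2.3 the same document applies the word diffuse to a scale of 4.0.

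Analysis 2 is meant to be compared with Analysis 1 (Miettinen-Nurminen, no prior) so that a gap between them can be put down to the handling of missing data. If the prior alone opens a gap when nothing is missing, the comparison no longer answers that question. The reference visit also matters. With Week 4 as reference, the Week 24 contrast is a main effect plus an interaction; with Week 24 as reference it is a single term with prior sd 1. The SAP does not say which applies.

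**Working it through.** **1. The plan's own prior summary.** Median: expit(−1.7) = 15.4%, stated as 15%. Mean of expit(N(−1.7, sd)): 31.2% for the baseline logit alone (sd 3) and 31.9% for the baseline plus one N(0, 1) effect (sd √10); stated as 32%. The 90th percentile of Inverse-Gamma(1, 1) is −1/ln 0.9 = 9.49, stated as about 9. The summary reproduces, and the 32% supports reading sd 1 as applying to visit effects.

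**2. Prior against planned effect.** SAP 2.2.1 plans a 24-point difference over 5% placebo.

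- Log odds ratio = ln[(0.29/0.71)/(0.05/0.95)] = ln 7.76 = 2.05.
- Week 4 reference, prior sd √2: z = 2.05/1.41 = 1.45, upper tail 7.4%.
- Week 24 reference, prior sd 1: z = 2.05, upper tail 2.0%.
- With sd 4 on each term the tails are 36% and 30%.

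These tails assume no random-intercept variance. With variance 1, 4 or 9 the conditional log odds ratio needed for 29% against 5% is 2.30, 2.96 or 3.83, further out in the prior.

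**3. Estimate read from the model, complete data.** From the documents: 6 arms, 5 visits, n = 120 per arm and pooled placebo (60 for 10 mg), and the stated priors. Assumed:

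- Random-intercept SD (τ) of 1, 2 or 3.
- Week 24 SALT ≤20 rates of 5/7/15/21/24/29% for placebo, 10, 30, 50, 200/30 and 200/50 mg.
- Share of the Week 24 rate reached at Weeks 4/8/12/18: slow 0.02/0.12/0.35/0.70, fast 0.10/0.30/0.55/0.80.

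The model was fitted to expected counts. Entries are posterior modes over the two profiles for 200/50 mg minus placebo (true value 24.0 points).

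| Prior sd, reference visit | τ = 1 | τ = 2 | τ = 3 |
|---|---|---|---|
| 1, Week 4 | 22.0–22.1 | 20.5–20.7 | 18.8–19.2 |
| 1, Week 24 | 19.1–19.6 | 17.0–17.4 | 14.9 |

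With sd 4 the range over all τ is 23.1–23.8 (Week 4) and 22.2–23.4 (Week 24). Placebo, truly 5%, is estimated at 6.0–9.8% with sd 1 and 5.1–6.3% with sd 4.

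Posterior means agree (slow profile, τ = 1/2/3). With sd 1 they are 21.6/20.3/19.3 (Week 4) and 18.9/17.2/14.4 (Week 24). With sd 4 they are 24.2/24.1/22.8 and 23.6/21.9/21.7.

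A second fit, with different assumed visit and arm rates and τ = 2/3/4, gave 20.9/19.3/18.1 (Week 4) and 17.2/15.0/13.6 (Week 24) with sd 1. With sd 4 it gave 23.8/23.1/22.7 and 22.9/21.9/21.3.

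**4. Does the conclusion flip?** The smallest posterior mean/SD for 200/50 mg on SALT ≤20 was 14.4/3.5 = 4.1 in the first set and 3.9 in the second. Both exceed 3.23, the normal quantile for two-sided 0.00125.

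**5. Model used only to impute.** Fall in the overall SALT ≤10 difference (25% against 5%, true 20.0 points) with sd 1, Week 24 values missing completely at random:

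| Imputed | Week 4 reference | Week 24 reference |
|---|---|---|
| 5% | 0.07–0.12 | 0.18–0.30 |
| 10% | 0.14–0.25 | 0.37–0.62 |
| 20% | 0.31–0.55 | 0.78–1.30 |

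With sd 4 the fall is at most 0.13 points at 10% and 0.28 at 20%. If Analysis 4 were instead read from the model, the second fit (τ = 3, Week 4 reference) turns 20 points into 15.9 with sd 1 and 19.4 with sd 4.

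**The case against.** - **Section 9.6 is headed tipping point, so its priors may not govern Analysis 2.** This is an inference, but a strong one. SAP 5.2.1.2 says the tipping point uses the same logit-normal model, no other prior for that model is given, and 9.6 lists seeds for PGI-C, for which Table 5 plans only Analysis 4.
- **Under 5.3.1(c) Analysis 2 is imputation, and the effect nearly vanishes.** Correct, and it is why the route must be stated. It does not rescue the analysis that 5.2.1.2 describes.
- **The tipping-point grid includes delta = 0, a MAR result by imputation that barely depends on the prior, and Analysis 3 uses none.** A careful reader could detect the prior effect from these. That lowers the risk of misreading without removing it.
- **Analysis 2 is supplementary, the shrinkage is towards no difference, and part of the range is below one standard error of the planned difference** (√[(0.29×0.71 + 0.05×0.95)/120] = 4.6 points). The first two stand and cap the importance. The third is the wrong yardstick, because both analyses use the same subjects and the gap is not independent sampling error.
- **The size rests on assumed inputs.** It does. The stated placebo bound has no value and was not modelled, and real zero cells were not tested. The direction was the same in every scenario run.
- **Sd 4 is borrowed from a different model and piles prior mass at extremes.** With Week 4 as reference, the prior sd for an active arm's Week 24 logit is √(9 + 3×16) = 7.5, which puts 55% of the prior response probability below 1% or above 99%, against 24% with sd 1. This is a real cost and a reason for convergence checks. Deleting the word diffuse instead would cure the wording but leave Analysis 2 unfit for its stated purpose.

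**Conclusion.** The concern holds. The SAP promises diffuse priors and specifies informative ones. Read from the posterior, Analysis 2 would fall below Analysis 1 by about 2 to 9 of 24 points with complete data (posterior modes, τ from 1 to 3, two assumed visit profiles), depending largely on a reference visit the SAP does not name. The 30, 50 and 200/30 mg differences are shrunk too; no conclusion was calculated for those arms.

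The consequence is bounded. Analyses 1 and 3 are untouched. Analyses 2a and 4a, and the EMA primary Analysis 4 as the SAP describes it, move by at most about 0.6 points at 10% imputed. The 200/50 mg conclusion stands. It should be fixed, but it does not threaten the primary result.

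**What to change.** In SAP 9.6:

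- Widen the treatment, visit and interaction priors from sd 1 to about 4 on the logit scale. The baseline-logit prior can stay.
- State the reference visit.
- State that these priors apply to Analyses 2, 2a, 4 and 4a.

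In SAP 5.2.1.2 and 5.3.1(c), state one route for Analysis 2: read from the posterior or run by imputation. Say plainly that Analysis 4 is run by imputation, so that the protocol's GLMM wording cannot be taken otherwise. A prior-sensitivity run would be a useful addition.

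The cost is SAP wording and a few macro constants before unblinding. Wider priors need closer convergence checks when placebo response is near zero. Some shrinkage remains at sd 4, up to about 2 points with Week 24 as reference (24.0 − 22.2 = 1.8).
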